#### **9.4.6. Secondary Efficacy Analyses**

The logistic regression model will be used to assess the superiority of ADX-2191 over standard-of-care in reducing the rate of recurrent retinal detachment. The covariate-adjusted difference in rate of recurrent retinal detachment and associated 95% CI will be summarized (Ge et al., 2011). The model will include a binary response variable (indicating recurrence of detachment or not), a treatment effect and stratification factor adjustment.

The secondary endpoint of the Best Correct Visual Acuity (BCVA) of change from level at Screening (Visit 1) to the level at Week 24 will be analyzed using an MMRM model. The MMRM model will be fit with Screening BCVA value, treatment, visit, and the interaction of treatment and visit. Change from Screening level of BCVA will be the dependent variable.

Subgroup analysis for BCVA will be conducted based on the following factors, if deemed necessary:

1. Lens status (phakia vs. aphakia vs. pseudophakia)
2. Prior recurrent retinal detachments ( $>3$  vs.  $\leq 3$ )
3. Longstanding retinal detachment ( $>1$  month) (yes vs. no)
4. Pre-operative macular scar or macular hole (yes vs. no)

Exploratory efficacy endpoints will be summarized by visit for descriptive statistics only. No statistical between-group comparison will be performed, unless otherwise specified.

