**Secondary Endpoints:**

- Comparison of retinal detachment rates across standard of care and drug-treated subjects.
- Best-corrected Visual Acuity (BCVA) change from Screening (Visit 1) level to Week 24 (as measured using an Early Treatment Diabetic Retinopathy Study [ETDRS] chart by masked technicians).

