## **3. INVESTIGATIONAL PLAN**

### **3.1. Overall Clinical Trial Design and Plan**

A Phase 3, multicenter, adaptive clinical trial comprised of approximately 100 evaluable eyes in Part 1 (Part 2 sample size will be determined after analysis of Part 1) at high-risk for recurrent retinal detachment due to PVR, or with OGI that may or may not have PVR.

- Subjects in the **Control cohort** (Part 1a only) will receive Standard Procedures only (defined in Section 7).
- Subjects in the **Intervention cohort** (Part 1a and 1b) will receive Standard Procedures and repeated intravitreal injections of ADX-2191 at a dose of 400 µg/0.05 mL for 16 weeks (Figure 1).

In Part 1a of the GUARD Study (prior to activation of Protocol Version 5.0, dated May 5 2021), eligible subjects will be randomized 1:1 intraoperatively to either the **Control** or **Intervention** cohort. Subjects in the **Control** cohort will receive Standard Procedures only. In Part 1b of this study (after activation of Protocol Version 5.0, dated May 5 2021), eligible subjects will no longer be randomized and all enrolled subjects will be placed in the **Intervention** Cohort. Subjects in the Intervention cohort will receive Standard Procedures and intravitreal ADX-2191 injections (Figure 1).

In Part 1a, stratification was used to balance treatment assignments within key subgroups. Subjects are to be stratified by clinical presentation (recurrent retinal detachment vs. OGI) and number of recurrent retinal detachments (>3 vs. ≤3).

Subjects enrolled in Part 1 will not be eligible to participate in Part 2 nor will they be eligible to be enrolled again during Part 1.

Clinical trial procedures to be conducted in Part 1 and Part 2 are outlined in the Schedule of Assessments (Table 1).

For Part 1, approximately 100 evaluable eyes must complete the 24-week clinical trial. Up to 50 additional subjects may be recruited to achieve the minimum number of evaluable subjects.

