In Part 1b of the GUARD study with activation of Protocol Version 5.0 (dated May 5 2021), eligible subjects will no longer be randomized and all enrolled subjects will be placed in the Intervention Cohort.

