## 7.2. Day 0/Operative Day/Enrollment (Visit 2)

- Review eligibility criteria (Section 6.2)
- Collect adverse events (Sections 6.6 and 8)
- Collect concomitant medications (Section 6.5)
- If applicable, perform pregnancy test (Section 6.7)
- Perform Pars Plana Vitrectomy (Section 6.9)
- Confirmation of enrollment prior to suturing the sclerotomies (Section 6.10)
  - To complete a subject's enrollment in the clinical trial, the surgeon must confirm intraoperatively that the retina has been completely reattached and that in the surgeon's best judgment, the subject has a high likelihood of benefitting from enrollment in the clinical trial.

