## **9. STATISTICS HYPOTHESES AND METHODS OF ANALYSES**

### **9.1. Clinical Trial Populations**

#### **9.1.1. Intent-to-Treat (ITT)**

The Intent-to-Treat (ITT) population consists of all subjects who were randomized. All data will be included, and no subjects will be excluded because of protocol violations. All data will be included, and no subjects will be excluded because of protocol violations; subjects who have retinal detachment within 1-week post-operatively who will be deemed to have failed Day 0 (surgery) and will be removed from the efficacy analysis as per protocol per Section 2.2.1.

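### The plan does not say which eyes enter the superiority comparison with standard of care, so non-randomized Part 1b eyes may be pooled against controls who exist only in Part 1a

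*Combined protocol and SAP*

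**What the plan says.** The synopsis lists as a secondary endpoint "Comparison of retinal detachment rates across standard of care and drug-treated subjects". Section 9.4.6 analyses it by logistic regression: "The logistic regression model will be used to assess the superiority of ADX-2191 over standard-of-care in reducing the rate of recurrent retinal detachment". The model has a binary response with "a treatment effect and stratification factor adjustment". The section names no analysis population and includes no term for Part 1a versus Part 1b.

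The two groups do not cover the same period. For the Control cohort Section 3.1 reads "Part 1a only) will receive Standard Procedures only (defined in Section 7"; for the Intervention cohort it reads "Part 1a and 1b) will receive Standard Procedures and repeated intravitreal injections of ADX-2191". From Version 5.0 on, per Section 3.2.2, "eligible subjects will no longer be randomized and all enrolled subjects will be placed in the Intervention Cohort".

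Section 9.1.1 gives a definition that would exclude Part 1b: "The Intent-to-Treat (ITT) population consists of all subjects who were randomized". Section 9.4.5 assigns that population to the primary efficacy analyses. Section 9.4.6 does not refer to it.

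Section 9.4.6 also plans an MMRM for change in best-corrected visual acuity, with screening value, treatment, visit and treatment-by-visit terms. Again no population is named.

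**The concern.** Randomization protects a comparison with control only while both groups come from the same randomized set. Part 1b eyes differ from Part 1a eyes in two ways that the design builds in.

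- **Calendar period.** Part 1b follows activation of Version 5.0, and no controls are enrolled in it.
- **Selection.** Section 7.2 completes enrolment during surgery, once the surgeon confirms that "the subject has a high likelihood of benefitting from enrollment in the clinical trial". In Part 1a the surgeon was to be blind to assignment at that point (Sections 3.2.2 and 6.10). In Part 1b the surgeon knows that every enrolled eye will receive drug.

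If the drug group includes Part 1b, either difference can pass for a treatment effect or hide one. Adjusting for clinical presentation or number of prior detachments does not help, because within each stratum the Part 1b eyes still have no concurrent control. The result would be a partly external-control comparison reported as superiority over standard of care, in a trial whose primary analysis already relies on a historical rate.

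**Working it through.** **1. The plan's own design figure.** Section 9.3.1 gives rates of 0.2 and 0.5, 45 per group, two-sided 0.05, about 80% power. Sample size without continuity correction: n = [1.96·√(2·0.35·0.65) + 0.8416·√(0.5·0.5 + 0.2·0.8)]² / 0.3² = (1.322 + 0.539)² / 0.09 ≈ 38.5, so 39 per group. With continuity correction: (38.5/4)·[1 + √(1 + 4/(38.5·0.3))]² ≈ 44.9, so 45 per group. Power at 45 per group is 80.1% with the correction, 81.5% by Fisher's exact test and 86.0% uncorrected. The stated figure reproduces; the sample size is not in question.

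**2. Which population do the passages imply?**

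- Towards pooling: the synopsis endpoint sets standard of care against drug-treated subjects with no limit to Part 1a. Section 9.4.5 uses the same term for the group compared with the historical rate, in what Section 9.3.1 now calls a single-arm study. Section 3.1 defines the Intervention cohort across both parts.
- Away from pooling: ITT means randomized subjects, and the model adjusts for stratification, which existed only in Part 1a.
- Unresolved: ITT is attached by name to the primary analysis only. Read literally there, it would remove every Part 1b eye from the single-arm estimate, so it needs revision. If it is widened to admit Part 1b, nothing in Section 9.4.6 prevents pooling.

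**3. Size of the bias if pooled.** Let n_a and n_b be the drug eyes from Parts 1a and 1b, with underlying rates on drug p_a and p_b. The pooled drug rate is (n_a·p_a + n_b·p_b)/(n_a + n_b), so the estimate shifts from the randomized contrast by

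shift = [n_b/(n_a + n_b)] × (p_b − p_a).

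The documents give neither the split nor p_b − p_a. Both are assumptions below. The total is held at the approximately 100 evaluable eyes of Section 9.3.1, with 1:1 allocation in Part 1a.

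- 35 control, 35 randomized drug, 30 Part 1b: 30/65 × 0.10 = 0.046.
- 25 control, 25 randomized drug, 50 Part 1b: 50/75 × 0.10 = 0.067.

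**4. Error rate and power over a range of splits.** Exact enumeration of an unadjusted two-proportion z-test (equivalently chi-square), two-sided 0.05. The false-win columns assume no drug effect, a rate of 0.5 in all Part 1a eyes, and a Part 1b rate lower by d. The power columns assume 0.2 versus 0.5 and no difference between parts.

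| Control / Part 1a drug / Part 1b drug | Shift per 10 points | False win, d = 0.10 | False win, d = 0.20 | Power, pooled | Power, Part 1a only |
|---|---|---|---|---|---|
| 15 / 15 / 70 | 8.2 points | 9.1% | 24.3% | 68% | 42% |
| 25 / 25 / 50 | 6.7 points | 9.2% | 22.8% | 82% | 64% |
| 35 / 35 / 30 | 4.6 points | 6.5% | 14.1% | 88% | 77% |
| 40 / 40 / 20 | 3.3 points | 5.5% | 10.1% | 89% | 82% |

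The nominal false-win rate in the drug's favour is 2.5%; with d = 0 enumeration gives 2.6% to 2.8%. If Part 1b eyes instead do worse by d, the shift has the same size and counts against the drug.

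**5. Would a Part 1a/1b term rescue the pooled model?** Not as a separate remedy. With no controls in Part 1b, such a term takes up the Part 1b level, and the treatment contrast is then estimated essentially from Part 1a alone.

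**The case against.** A reader might infer that the plan commits to comparing all drug-treated eyes with the controls. The documents do not say that. Section 9.4.6 names no population, the phrase about drug-treated subjects stands in the synopsis, and neither place says all. If ITT governs Section 9.4.6, the comparison is already the randomized one. The stratification adjustment fits that reading. Sections 9.4.1 and 9.4.9 also make a later SAP the final determinant, and no separate SAP text is available to show what it does. This stands: the defect is an open choice, not a stated decision to pool.

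It is also tempting to say that pooling would favour the drug. Nothing fixes the sign: surgeons certain of giving drug might enrol worse eyes as easily as better ones. Nor is open-label treatment what separates the parts, since the surgeon learns the assignment at the end of surgery in Part 1a too. Only foreknowledge at enrolment and calendar time differ, and central confirmation of imaging eligibility in both parts narrows the surgeon's discretion without removing it.

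Nor does the point threaten the trial's success criterion. Section 9.4.3 says that one hypothesis is tested, and Sections 9.2 and 9.4.5 make it the historical-control comparison. Section 2.2.2 lists only visual acuity as secondary, so even the status of the detachment comparison differs from the synopsis.

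Finally, restriction costs 11 to 18 points of power in the two central scenarios, which is not trivial. But the extra power from pooling is sound only if Part 1b eyes do not differ from Part 1a eyes apart from treatment. The drug eyes of the two parts can be compared as a weak check; controls cannot.

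**Conclusion.** The concern holds as a gap in specification with a real consequence. The population for the superiority comparison with standard of care is undefined, the text permits pooling non-randomized eyes against Part 1a controls, and the model as listed cannot separate period or selection from treatment if that is done. The same applies to the treatment term in the visual acuity MMRM.

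The shift equals the Part 1b share of drug eyes times the rate difference between parts: 4.6 and 6.7 points per 10-point difference at the 30/65 and 50/75 splits, in either direction. The splits and the difference are assumptions, and the error rates and powers are for an unadjusted test, not the planned covariate-adjusted one. The documents do not support a claim that the sponsor will pool, that the result would be biased in the drug's favour, or that the primary conclusion is affected. This is a cheap improvement that should be made.

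**What to change.** In Section 9.4.6 and the SAP, state that the inferential logistic and MMRM comparisons with control use only subjects randomized in Part 1a, analysed as randomized and adjusted for the stratification factors (the MMRM terms now listed include none). Report any pooled Part 1a and 1b comparison as supportive and label it non-randomized.

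Two alignments belong with this: define a separate drug-treated set for the historical-control analysis, so that revising ITT for that purpose does not change the control comparison by default; and make the secondary endpoints in Section 2.2.2 agree with the synopsis.

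The cost is a sentence or two of text and lower power in a secondary analysis. At 0.2 versus 0.5 and the assumed sizes, power falls from 88% (65 drug, 35 control) to 77% (35 and 35), or from 82% (75 drug, 25 control) to 64% (25 and 25). No data are lost, because the pooled result is still reported.

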### **3.2.2. Randomization**

Per screening evaluations, all subjects will require a confirmation from the CRC and Medical Monitor that they meet the retinal imaging inclusion criteria to be eligible. If urgent (<24 hours) CRC verification is required, the Medical Monitor may unilaterally review the images and authorize the planned enrollment. In the event there is a discrepancy between the CRC and Medical Monitor review, the Medical Monitor determination will be the study-accepted reading of accountability. In Part 1a, eligible subjects are randomized to either standard procedure or standard procedure with intervention. This randomization is a 1:1 ratio within the stratified cohort groups. In Part 1b, subjects must still meet all inclusion criteria prior to enrollment. This verification process provides an additional level of objectivity in assuring subject qualification for participation in the clinical trial. If the photographic image is too poor in quality to verify eligibility, then the subject will be noted as screen failures. As noted in Section 6.8.5, in cases where preoperative color photography is technically difficult for image acquisitions (i.e., dense lens opacity, constricted pupil, intraocular bleeding, etc.), then intraoperative imaging using the operative microscope is allowed.

In Part 1a, those subjects that meet enrollment criteria will enter the randomization process and will be allocated to the Control vs. Intervention cohorts. The assignment to cohort will be

revealed intraoperatively at the conclusion of the surgery to the investigator after retinopexy has been applied. Note: administratively, the randomization may occur prior to surgery if logistically required by the site. However, the investigator must remain blinded to randomization until the defined timepoint. When administrative randomization occurs prior to surgery, all measures must be taken to avoid indicating assigned treatment group prior to conclusion of surgery.

Randomization scheme will be managed by an Interactive Response Technology (IRT) system. Subjects will be randomized by indication (recurrent retinal detachment due to PVR or any RD associated with OGI).

Eligible subjects will be randomized 1:1 intraoperatively to either group:

**Control:** Standard Procedures

**Intervention:** Standard Procedures with the addition of repeated intravitreal injections of ADX-2191 until post-operative Week 16.

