## **9.3. Sample Size**

### **9.3.1. Sample Size Part 1**

The initial design of the GUARD Study was based on an recurrent retinal detachment rates of 0.2 and 0.5 for ADX-2191 and standard-of-care group, respectively. With a sample size of 90 subjects (45 per group) and 2-sided significant level at 0.05, the clinical trial would have approximately 80% power to detect the superiority of ADX-2191 over the standard-of-care.

The protocol was updated to an open-label, single arm study in Version 5.0.

Approximately 100 evaluable eyes will be recruited to complete the 24-week treatment period.

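### The BCVA mixed model leaves out the Part 1a stratification factors that the logistic model in the same section adjusts for

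*Combined protocol and SAP*

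**What the plan says.** Section 9.4.6 describes two model-based secondary comparisons. The logistic model for recurrent detachment has "a treatment effect and stratification factor adjustment". The BCVA model is given as a list of terms: "The MMRM model will be fit with Screening BCVA value, treatment, visit, and the interaction of treatment and visit". No stratification factor is in that list. The number of prior detachments (>3 vs ≤3) appears only as an optional BCVA subgroup factor. Clinical presentation appears nowhere in the BCVA analysis.

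On allocation in Part 1a, Section 3.1 (and the Synopsis, Overall Design) names two factors: "Subjects are to be stratified by clinical presentation (recurrent retinal detachment vs. OGI) and number of recurrent retinal detachments", the second cut at >3 vs ≤3. Section 3.2.2 confirms that allocation was balanced within strata ("This randomization is a 1:1 ratio within the stratified cohort groups") but then names one factor only: "Subjects will be randomized by indication (recurrent retinal detachment due to PVR or any RD associated with OGI". Section 9.4.6 refers to the stratification factor in the singular.

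On Part 1b, Section 3.2.2 says that "eligible subjects will no longer be randomized and all enrolled subjects will be placed in the Intervention Cohort". Section 9.3.1 adds: "The protocol was updated to an open-label, single arm study in Version 5.0". Control eyes therefore come from Part 1a alone. Section 9.4.6 does not say which eyes enter the BCVA comparison.

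**The concern.** Two models in one section analyse the same design differently. The sponsor judged presentation and detachment history important enough to balance at randomization and to adjust for in the detachment model. If they also predict visual recovery, leaving them out of the BCVA model has one of two effects, depending on the analysis set.

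- **Part 1a only.** The arms are balanced on the strata by design. Leaving prognostic strata in the residual does not bias the estimate, but the model-based standard error is too large. The interval is wider than it needs to be and covers more than 95% of the time.
- **Part 1b pooled with Part 1a.** The added drug eyes were not allocated at random, so the case mix can differ between drug and control. The omission can then move the estimate itself.

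What is at stake is the precision, or the accuracy, of the only secondary endpoint that measures visual function.

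**Working it through.** **The plan's own figure.** The only power statement (Section 9.3.1) is for the detachment rate: 0.2 vs 0.5, 45 per group, two-sided 0.05, about 80% power. Without continuity correction, n = [1.96·√(2·0.35·0.65) + 0.842·√(0.2·0.8 + 0.5·0.5)]² / 0.3² = 38.5, so 39 per group. With the correction it is 45 per group, and power at 45 is 80.1% (Fisher's exact test: 81.5%). The figure reproduces. It says nothing about BCVA: the protocol gives no BCVA standard deviation, target difference, power or stratum effect.

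**Case A: Part 1a only, randomized within strata.**
Let R2 be the share of residual variance that the strata explain beyond Screening BCVA (assumed: 0 to 0.20). With treatment balanced within strata, width without adjustment / width with adjustment = 1/√(1 − R2). This was checked by simulating a Week 24 analysis of covariance, a single-visit simplification of the MMRM, with 90 eyes, 1:1 allocation within three strata of assumed size, and 4,000 runs per setting.

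| Assumed R2 | Extra width, formula | Extra width, simulated | Coverage without strata | Coverage with strata |
|---|---|---|---|---|
| 0 | 0% | 0.0% | 94.9% | 94.9% |
| 0.05 | 2.6% | 2.5% | 95.9% | 95.2% |
| 0.10 | 5.4% | 5.5% | 96.4% | 95.6% |
| 0.20 | 11.8% | 11.9% | 96.9% | 94.8% |

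The error is conservative throughout. It is nil if the strata add nothing to Screening BCVA.

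**Case B: Part 1b drug eyes pooled.**
The bias left by omitting a factor is the difference in stratum mix between drug and control, times the difference in BCVA change between strata at equal Screening BCVA. Both inputs are assumptions:

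- 5 percentage points × 5 letters = 0.25 letters
- 10 points × 10 letters = 1 letter
- 20 points × 10 letters = 2 letters
- 30 points × 15 letters = 4.5 letters

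The sign depends on which arm has more eyes with the poorer outlook, which the documents do not tell us.

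The width formula fails here because the factor is correlated with treatment. For illustration, assume two-thirds of eyes are on drug and open globe injury makes up 30% of drug eyes and 10% of controls:

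- Overall share of open globe injury: 2/3 × 0.30 + 1/3 × 0.10 = 0.233.
- Squared correlation of stratum with treatment: (2/9 × 0.20)² / (0.233 × 0.767 × 2/9) ≈ 0.05.
- Variance inflation from adjusting: 1/(1 − 0.05) ≈ 1.05.

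At R2 = 0.05 the variance ratio, adjusted to unadjusted, is about 0.95 × 1.05 = 1.00. There is no gain in precision. In this case the reason to adjust is bias, not width.

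**The case against.** The strongest reply has four parts.

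1. **The loss of precision is not documented.** A reader might infer that the BCVA intervals are certainly too wide, or that a fixed part of the sample is wasted. The documents do not support this. Screening BCVA is already in the model, nothing shows how much the strata add to it, and zero is a possible value. This stands.
2. **Pooling is not documented.** A reader might infer that the BCVA comparison is confounded by Part 1b. Section 9.4.6 names no analysis set, and Section 9.1.1 defines the ITT population by randomization, which read literally excludes Part 1b. The bias is therefore conditional on pooling. Nor may the two harms be added together, since each belongs to a different analysis set. This stands too, and it is why the analysis set has to be stated.
3. **Section 9.4 is a summary that defers to a SAP** (Sections 9.4.1 and 9.4.9). This is fair as to what the final model may contain. But no separate SAP text is in the documents, and the protocol lists the model terms explicitly. Deferral is an opportunity to correct that list; it does not correct it.
4. **The impact is small.** Section 9.4.3 says that only one hypothesis is tested, and by Sections 9.2 and 9.4.5 that is the comparison with the historical control. BCVA decides no success criterion, and in Part 1a the omission errs on the safe side. This limits the weight of the point but is no reason to keep the inconsistency.

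**Conclusion.** The omission is certain: the BCVA model lists no stratification factor, while the logistic model beside it adjusts for stratification. Its size is not known. For a Part 1a comparison the intervals are 0% to about 12% wider than with adjustment, over an assumed R2 of 0 to 0.20, and conservative. If Part 1b is pooled, the consequence is possible bias in either direction: 0.25 to 4.5 letters in the examples shown, all on assumed inputs. Adjustment would then reduce the bias from these factors only and would not make the comparison randomized. This is a free improvement on a secondary endpoint outside the tested hypothesis. It does not threaten the trial's primary conclusion.

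**What to change.** Make three changes in the SAP before database lock.

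1. Reconcile Section 3.1 and the Synopsis (two stratification factors) with Section 3.2.2 (indication only), and state which factors the allocation system used. The adjustment in the logistic model needs the same clarification.
2. Add clinical presentation (recurrent detachment vs open globe injury) and number of recurrent detachments (>3 vs ≤3) to the BCVA MMRM, matching the logistic model. Enter them as main effects, since a crossed factor may have sparse cells.
3. State whether the BCVA comparison uses Part 1a alone or pools Part 1b. If it pools, say that the comparison is not fully randomized.

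A Screening BCVA-by-visit interaction is optional and not part of this point.

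The cost is two degrees of freedom and a few lines of text. No new data are needed: eligibility review already establishes presentation (inclusion criterion 2) and requires the detachment history (exclusion criterion 10), in Part 1b as in Part 1a.
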